5.3.4. Point of enrolment

Patients will be recruited through in-patient wards across multiple European centres. Approximately one (1) patient every four (4) months per centre will be recruited with an estimated three (3) patients per centre in total, although competitive recruitment will be utilised. This recruitment strategy is based upon the data accumulated during the performance of the CANONIC study [5].

Following consent and confirmation of eligibility, patients will be randomised electronically via the eCRF . The site will be issued with the subject ID number and informed of their treatment arm. Patients will be deemed enrolled at the point of randomization (Day 0).

5.3.5. Total expected duration of the clinical investigation.

The total duration of the study will be approximately 39 months.

5.3.6. Expected duration of each subject's participation.

After signing the Informed Consent, the patient can be screened for compliance with the in/exclusion criteria for up to 3 days. Patients from cohort 1, 2 and 3 are followed for 28 days, those from cohort 4 and 5 for 90 days.

Patients will be randomized on study day 0 followed by a maximum treatment window period of 10 days (DIALIVE arm). All patients will be intensively followed during the initial 28 days post-randomization and complete the study after completion of study day 28 (cohort 1, 2 and 3) or day 90 (cohort 4 and 5)...

5.3.7. Number of subjects included in the clinical investigation.

30 evaluable subjects will be randomised to receive either standard of care (SOC) or treatment with DIALIVE (1:1 randomisation).

As this is a first-in-man trial, and no hypothesis is to be tested, the sample size is arbitrarily set to obtain adequate information in a small patient population. This reduces the total number of patients exposed to potential study related risks while allowing the investigators to learn maximally from this potential treatment for ACLF-patients for which no alternative

Clinical Investigation Plan	CIP YAQ-002	Version: 7.0 10 October 2019
-----------------------------	-------------	------------------------------

treatment exists and the Data Safety Monitoring Board to make appropriate decisions on study (dis)continuation by comparing occurrence of adverse events between control and treatment arms in each of the 5 cohorts of patients.

5.3.8. Estimated time needed to select this number (i.e. enrolment/recruitment period).

There is an estimated 39 months recruitment period that has been assigned. Start was on February 2017 and patient recruitment is anticipated to run till December 2019.

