Primary End Point	To evaluate the safety of the DIALIVE in patients with Acute on chronic liver failure (ACLF)	The percentage of subjects who experience at least one (1) serious adverse event (SAE) between study Day 1 and Day 10; especially the incidence rate of SAE in both arms of the study at Day 1 and Day 10. The percentage of subjects who discontinued DIALIVE due to a serious adverse device event (SADE) between Day 1 (first day of treatment) and Day 10 (DIALIVE arm only).
Secondary End Point(s)	To evaluate the impact of biochemical performance outlined hereunder towards clinical benefit for patients receiving DIALIVE treatment plus Standard of Care vs Standard of Care alone	 Mortality: 28-days and 3 months Change in ACLF Grade Change in CLIF-ACLF score Improvement in individual organ function: brain (HE), kidney (serum creatinine), CVS (mean arterial pressure), pulmonary (P/F ratio or S/F if arterial blood gas info is not available), liver (serum bilirubin) and coagulation (INR and platelet levels). Status of ICU and Hospital Discharge (including discharge to a hospice for palliative care). Lengths of stay in ICU and hospital at D28 and D90. ICU and hospital re-admissions with another episode of ACLF up to 90 days post randomization.

Clinical Investigation Plan	CIP YAQ-002	Version: 7.0 10 October 2019
-----------------------------	-------------	------------------------------

Secondary end	Objectives	Outcomes Measures
Point(s)	To evaluate the performance of the DIALIVE in patients with ACLF	 Change in Plasma endotoxin level (endotoxin activity and endotoxin concentration) between; Study D1,D3, D5 and D10 across SOC arm
		2. Study D1, D3, D5 and D10 across DIALIVE arm
		Start and end of a treatment session with
		DIALIVE on D1, D2 and D3 4. Study D1, D3, D5 and D10 between SOC and DIALIVE arms for patients with the same grade of ACLF at the time of inclusion in the study
		Target-Value (TV): 40% reduction; Acceptable-Value (AV): 20% reduction Change in Albumin function (Human non- mercapt albumin -2 (HNA-2) / Human marcapt albumin (HMA) ratio:
		5. Study D1, D3, D5 and D10 across SOC arm6. Study D1, D3, D5 and D10 across DIALIVE
		arm 7. Start and end of a treatment session with DIALIVE on D1, D2 and D3.
		8. Study D1, D5 and D10 between SOC and DIALIVE arms for patients presenting with the same grades of ACLF
		TV: 40% reduction; AV: 20% reduction

Clinical Investigation Plan CIP YAQ-002 Version: 7.0 10 0	October 2019
---	--------------

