5.1.3 Secondary End Points

To evaluate the performance of the DIALIVE in patients with ACLF. This is measured by;

Change in Plasma endotoxin level (endotoxin activity and concentration) between;

D1, D3, D5 and D10 across SOC arm $\,$

D1, D3, D5 and D10 across DIALIVE arm

_

¹⁰ In case a patient's treatment is discontinued, the follow up period will remain 28 days from the moment of randomization.

Clinical Investigation Plan	CIP YAQ-002	Version: 7.0 10 October 2019
-----------------------------	-------------	------------------------------

Start and end of a treatment session (on D1, D2 and D3) with DIALIVE D1,D3, D5 and D10 between SOC and DIALIVE arms for patients presenting with the same grades of ACLF (i.e. Grade 1 ALCF compared with Grade 1 ACLF)

Target-Value (TV): 40% reduction; Acceptable-Value (AV): 20% reduction at end of treatment cycle.

• Change in Albumin function (Human non-mercapt albumin -2 (HNA-2) / Human marcapt albumin (HMA) ratio:

D1, D3, D5 and D10 across SOC arm
D1,D3, D5 and D10 across DIALIVE arm
Start and end of a treatment session (on D1, D2, D3) with DIALIVE
D1,D3, D5 and D10 between SOC and DIALIVE arms for patients presenting with the same grades of ACLF (i.e. Grade 1 ALCF compared with Grade 1 ACLF)

TV: 40% reduction; AV: 20% reduction at end of treatment cycle.

- Mortality: 28-days and 90 days
- Change in ACLF Grade
- Change in CLIF-ACLF score
- Improvement in individual organ function: Brain (HE), Kidney (creatinine), CVS (mean arterial pressure), Pulmonary (P/F ratio, or S/F if patient is not intubated), Liver (serum bilirubin) and coagulation (INR and platelets).
- Status at ICU and Hospital Discharge (including discharge to a hospice for palliative care).
- Lengths of stay in ICU and Hospital at D28 and D90
- ICU and Hospital re-admissions with another episode of ACLF up to 3 months after randomisation.

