5.1.6. Equipment to be used for assessing the clinical investigation

All equipment except for the DIALIVE device, the EAA luminometer for endotoxin analysis, and the Primsmaflex platform¹¹ will be the property of the Investigator(s) and/or institutions and maintained and calibrated according to institutional guidelines. Records of maintenance and calibration will be made available at the Sponsor's request.

5.1.7. Replacement of subjects.

30 evaluable patients will be recruited across all sites to receive either treatment using the DIALIVE or SOC. Screen failures will be replaced to achieve an even balance in each cohort. The patient numbers will be increased and replaced if there are dropouts during the treatment period to allow 30 evaluable patients to be included. Dropouts can be i) patients who withdraw their consent, ii) patients who are considered 'not evaluable' because of an incomplete dialysis cycle (for DIALIVE patients) or iii) if a patient dies in the 10-day period following randomization to the SOC-arm, or iv) patients who are excluded based on a stopping rule.

A dropout rate of 17% is anticipated on the basis of observations made during execution of this study in the first 2 cohorts of patients. Patients who drop-out for reasons of an incomplete dialysis cycle are followed up for a duration of 28 days post-randomization.

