5.4. Procedures

See Schedule of assessments below for Standard of Care and DIALIVE Patients:

General overview of study design

Clinical Investigation Plan	CIP YAQ-002	Version: 7.0 10 October 2019
-----------------------------	-------------	------------------------------

SOC Patients	Prior Screening	Screening		Study Days							
Study Procedures		0-72hrs	Day 0	Day 1	Day 3	Day 5	Day 10	Day 14 +/- 2 days	Day 28 +/- 5 days	Day 90 +/- 5 days	
Informed consent ¹⁵	Х										
Inclusion/exclusion criteria		Х	X ¹⁶								
Demographics		Х									
Medical history		Х									
Complete physical examination		Х		Х	Х	Х	X	Х	X		
Weight (kg) and height (cm)		Х		Х	Х	Х	X	Х	Х		
Vital signs		Х		Х	Х	Х	X	Х	Х		
12-lead ECG		Х		Х							
Viral screen (local laboratory) ¹⁷		X									
Clinical laboratory (local laboratory) ¹⁸		X		Х	X	X	X	X	Х		
Full infection screen (local laboratory)		Х		Х		Х	X				
Pregnancy test (women only)		Х									
Coagulation (local laboratory) ¹⁹		X		Х	X	X	X	X	Х		
Randomisation			X								
AE assessments				Х	X	Х	X	Х	X	X ²⁰	
Concomitant medications				Х	Х	Х	X	X	Х		
CLIF-C OF Score, CLIF-C ACLF score, ACLF grade		Х		Х	X	Х	X	Х	X		

¹⁵ Informed consent must occur before ANY study specific procedures commence. Thorough clinical examination and assessment of FBC, U&Es, LFTs, Coagulation must be repeatedn if the test have been undertaken > 24 hours before randomization. Microbiology results obtained within the previous 72 hrs prior to screening may be used and samples not repeated. Viral serology results obtained within 8 weeks prior to screening maybe used and samples not repeated. Liver imaging results obtained 6 weeks prior to screening maybe used and tests not repeated unless there has been a significant change in clinical status 16 Confirmation only. Document in medical notes.

¹⁷ Tests performed: HBsAg, anti-HCV, and anti-HIV. Viral serology results obtained within 8 weeks prior to screening maybe used and samples not repeated.

¹⁸ Standard haematology and biochemistry as per local practice (Including CRP). 19 Tests performed: Platelets, PT, INR, PTT, Fibrinogen

Survival data only via a telephone call.

Clinical Investigation Plan CIP YAQ-002	Version: 7.0 10 October 2019
---	------------------------------

SOC Patients	Screening			tudy Days	ly Days				
Study Procedures	0-72hrs	Day 0	Day 1	Day 3	Day 5	Day 10	Day 14 +/- 2 days	Day 28 +/- 5 days	Day 90 +/- 5 days
MELD, MELD-Na	Х		X	Χ	X	Χ	X	X	
Pugh and Lille Scores	Х		Х	Х	Х	Х	X	Х	
eGFR	Х		Х	Х	Х	Х	X	Х	

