²⁵ Informed consent must occur before ANY study specific procedures commence. Thorough clinical examination and assessment of FBC, U&Es, LFTs, Coagulation must be repeated if the test have been undertaken > 24 hours before randomization. Microbiology results obtained within the previous 72 hrs prior to screening may be used and samples not repeated. Viral serology results obtained within 8 weeks prior to screening maybe used and samples not repeated. Liver imaging results obtained 6 weeks prior to screening maybe used and tests not repeated unless there has been a significant change in clinical status. s
26 Confirmation only. Record in medical notes.

²⁷ Blood pressure (supine), respiratory rate, body temperature will be recorded throughout DIALIVE treatment (as per Standard of Care)

²⁸ Tests performed: HBsAg, anti-HCV, and anti-HIV. Viral serology results obtained within 8 weeks prior to screening maybe used and samples not repeated

²⁹ Standard haematology and biochemistry as per local practice (including CRP). Performed throughout DIALIVE treatment as per local practices.

³⁰ Tests performed: Platelets, PT, INR, PTT, Fibrinogen. Performed throughout DIALIVE treatment as per local practices.

Clinical Investigation Plan	CIP YAQ-002	Version: 7.0 10 October 2019
-----------------------------	-------------	------------------------------

DIALIVE Patients	Screening	Treatment period									
Study Procedures	0-72hrs	Day 0	Day 1 ³¹	Day 2	Day 3	Day 5	Day 10	Day 14 +/- 2 days	Day 28 +/- 5 days	Day 90 +/- 5 days	
AE assessments			Х	X	X	X	X	X	X	X ³²	
Concomitant medications			Х	Х	Х	Х	Х	X	X		
CLIF-C OF Score, CLIF-C ACLF score, ACLF grade	Х		Х	Х	Х	Х	Х	Х	X		
CLIF-AD Score (if relevant)	Х		Х	Х	Х	Х	Х	Х	X		
MELD, MELD-Na	Х		X	X	Х	X	Х	Х	X		
Pugh and Lille Scores	Х		X	X	X	X	Х	Х	X		
eGFR	Х		Χ	X	Х	X	Х	Х	X		
West Haven grade	Х		Х	X	Х	Х	X	X	X		

³¹ DIALIVE treatment must commence before end of day 1. DIALIVE treatment may commence at day 0 at the discretion of the investigator. If DIALIVE treatment commences on Day 0, then Day 1 tests must be performed before treatment commences on Day 0 and therefore does not need repeating on Day 1.

32 Survival only via telephone call

Clinical Investigation Plan	CIP YAQ-002	Version: 7.0 10 October 2019
-----------------------------	-------------	------------------------------

DIALIVE Patients-During Treatment

Study Procedures	0-72hrs Screening	Day 0 ³³ Randomisation	Day 1 – day 10 Treatment Period	Day 14 +/- 2 days	Day 28 +/- 2 days

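### Day 90 length of stay and 90-day ACLF re-admission are secondary endpoints, but the only Day 90 contact is a survival-only call, and the protocol conflicts on whether early stoppers in cohorts 4 and 5 get that call

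*Protocol*

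**What the plan says.** **Endpoints.** Section 5.1.3 lists "Lengths of stay in ICU and Hospital at D28 and D90" as a secondary endpoint, and the synopsis lists "ICU and hospital re-admissions with another episode of ACLF up to 90 days post randomization". Mortality at 28 and 90 days is also secondary.

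**What is collected.** In Section 5.4 the Day 90 column has one mark in each arm's schedule, on the adverse event row. The footnote for standard of care (SOC) reads "Survival data only via a telephone call"; the one for DIALIVE reads "Survival only via telephone call". Neither schedule has a row for discharge, length of stay or re-admission.

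**How long patients are followed.**
- Section 5.3.6: "Patients from cohort 1, 2 and 3 are followed for 28 days, those from cohort 4 and 5 for 90 days". The next paragraph applies the same completion days to all patients, with no exception for those who stop early.
- Footnote 10 to Section 5.1.2: where a patient's "treatment is discontinued, the follow up period will remain 28 days from the moment of randomization".
- Section 5.1.7: "Patients who drop-out for reasons of an incomplete dialysis cycle are followed up for a duration of 28 days post-randomization".
- Section 2.2: at least 28 days for screen failures and excluded patients.
- Synopsis: a Day 90 assessment in the visit list and three months per patient, with no split by cohort.

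**Analysis.** Section 6 analyses every randomised patient who received any treatment, uses available data only and imputes nothing.

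**The concern.** Two secondary endpoints run to Day 90, yet the only contact planned after Day 28 is expressly confined to whether the patient is alive. A site that follows the schedule exactly does not collect what those endpoints need. Whatever is obtained would depend on local habit, so completeness could differ between sites.

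The second problem is the follow-up rule. For a cohort 4 or 5 DIALIVE patient who stops early, one section requires Day 90 and two other places say 28 days. If sites use the shorter period, 90-day status goes missing because treatment failed, and only in the DIALIVE arm, since SOC has no incomplete-cycle rule. Those patients remain in the analysis population and nothing is imputed, so the comparison of 90-day mortality between arms could be distorted in an unknown direction.

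**Working it through.** The protocol gives no figure to reproduce here: the sample size is set without a formula and no test is planned. The check compares passages, with supporting arithmetic.

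**1. Can another route supply the endpoints?** Section 12.1 counts hospitalisation following serious deterioration as a serious adverse event, and Section 12.4.1 requires such events to be entered in the eCRF. Two rules weaken this for the endpoint in question. Section 12.1 does not treat the studied disease as an adverse event unless it is more severe than expected. Section 12.5 does not record further events of an existing condition unless the investigator judges it worse than at baseline. A re-admission with ACLF no worse than at baseline can therefore go unreported. Discharge dates after Day 28 have no scheduled route at all.

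**2. How much of the window is affected?**
- 90 − 28 = 62 days; 62/90 = 68.9%.
- With ±5 days at both visits: 85 − 33 = 52 days to 95 − 23 = 72 days. The during-treatment table for DIALIVE gives ±2 days at Day 28, so the window is not uniform.
- This is calendar time, not a share of events.

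**3. Whom do 90-day data concern?** Section 5.2 sets five cohorts of six, three per arm. Cohorts 4 and 5 give 2 × 6 = 12 of 30 evaluable patients (40%), six per arm.

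**4. How many could stop early?**
- Appendix 7 B: 2 of 8 DIALIVE patients were non-evaluable, 2/8 = 25% (exact 95% CI 3.2% to 65.1%).
- Section 5.1.7 anticipates 17% dropout, which agrees with 2/12 = 16.7% (two dropouts per 12 evaluable patients). That match is an inference.
- Expected in cohorts 4 and 5: 12 × 0.17 = 2.04 dropouts. Alternatively, 6/(1 − 0.25) = 8 treated DIALIVE patients for six evaluable, so two early stoppers.

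**5. What would missing status do to 90-day DIALIVE mortality?** With N = 8 treated, k known deaths and m unknown statuses, mortality lies between k/8 and (k + m)/8. The width is m/8, whatever k is:

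| m | Width |
|---|---|
| 0 | 0 points |
| 1 | 12.5 points |
| 2 | 25 points |

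**6. When is the loss zero?** When early stoppers die before Day 28, because their 90-day status is then known. Appendix 7 B reports two DIALIVE deaths within 24 to 36 hours of starting treatment. It does not say outright that these were the two non-evaluable patients. If they were, no 90-day mortality status would have been lost among non-completers so far.

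**The case against.** The strongest reply is that a schedule of visits and tests is not a list of everything collected. Day 28 stay and discharge status have no row either. Section 5.1.5 has all data recorded in source documents and the eCRF, and Section 7.1.1 names medical and nursing notes as source. The eCRF, the study overview figure and the Appendix 8 illustrations could not be seen. This stands as a limit: it cannot be said that the data will not be collected, only that the protocol does not arrange it. It does not remove the point, because up to Day 28 there are study visits with adverse event assessment, whereas the one later contact is explicitly confined to survival.

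On follow-up, the 28-day statements can be read as specific exceptions to a general rule, and the minimum in Section 2.2 fits either reading. The version 6.0 entry in Appendix 9 lists both the dropout follow-up and the three-month extension, which could suggest a deliberate split. The same appendix shows, however, that the 28-day dropout wording was already in an earlier country amendment, before any 90-day follow-up existed. Even a deliberate split would lose Day 90 status in one arm only.

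It is also fair that the percentage-point widths depend on assumed numbers, that how often the safety-reporting exclusions would apply is unknown, and that the missing cohort limit in the synopsis and endpoint lists is editorial.

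**Conclusion.** The point holds. Followed as written, the protocol leaves Day 90 stay and 90-day ACLF re-admission without reliable collection over 62 of 90 days, and it gives conflicting instructions on Day 90 follow-up of cohort 4 and 5 DIALIVE patients who stop early.

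The possible effect on 90-day DIALIVE mortality is 0 to 25 points of indeterminacy. This assumes about 8 treated DIALIVE patients in cohorts 4 and 5, early stopping at the rate seen in cohorts 1 and 2, and sites applying the 28-day wording. The sign of any bias is unknown.

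The stakes are limited: the affected endpoints are secondary and descriptive, they concern 12 evaluable patients, and the Day 1 to 10 primary endpoint is untouched. It should be corrected, with medium confidence given the documents that could not be seen.

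**What to change.** 1. In both Section 5.4 schedules, extend the Day 90 call to ICU and hospital discharge dates and any ACLF re-admission with its date. Otherwise delete the Day 90 stay and 90-day re-admission endpoints from the synopsis and Section 5.1.3.
2. State that every randomised patient in cohorts 4 and 5 has the Day 90 call whatever the treatment status, unless consent is withdrawn. Reconcile Section 2.2, footnote 10 to Section 5.1.2, Section 5.1.7 and Section 5.3.6 accordingly.
3. Note in the synopsis (endpoints, visits, duration) and Section 5.1.3 that Day 90 follow-up and the 90-day endpoints apply to cohorts 4 and 5.

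The cost is a few questions on an existing call, about one or two more calls in the DIALIVE arm, and short wording changes. Dates and re-admissions reported by telephone may need checking against hospital records, and it becomes plain that the 90-day sample is 12 evaluable patients, not 30.

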Acute decompensation (AD) or cirrhosis complicated with organ failure (ACLF) has a mortality rate of 30-40% and death is mostly related to multiple organ dysfunction [5]. The condition is widespread, affecting about 30% of all hospitalised cirrhotic patients and has a 28-day mortality of about 30% [6, 7]. Furthermore, ACLF occurs in young patients (mean age 52 years) and about 50% have no knowledge of their underlying cirrhosis. Indeed, in about 40% patients, no precipitating event can be identified. A prospective observational study of hospitalized patients with cirrhosis in 2013 by the European Association for the Study of the Liver-Chronic liver failure (EASL-CLIF) Consortium, the EASL-CLIF Acute-on-Chronic Liver Failure in Cirrhosis (CANONIC), the largest and most comprehensive registry on ACLF to date, showed a 28 day

Clinical Investigation Plan	CIP YAQ-002	Version: 7.0 10 October 2019
-----------------------------	-------------	------------------------------

mortality of 22%, 32% and 78% for ACLF grades 1, 2 and 3, respectively. [6]. The diagnosis of ACLF is made using the CLIF Consortium organ failure scores (CLIF-C OFs), the prognosis of these patients using the CLIF Consortium ACLF score (CLIF-C ACLF), and ACLF severity grades defined using the CLIF-OF organ failure score [8], In the CANONIC study two organs, the kidneys and the brain, were found to be of particular significance in determining short term mortality. More recent studies suggest that even milder degrees of renal impairment in cirrhosis, not in the 'failure' range of the CLIF-OF scoring system, may be associated with development of ACLF and significant mortality. This refers to the subgroup(1b) of stage 1 AKI defined by a serum Creatinine (sCr) at presentation of above 1.5 mg/dL [9]. As for brain dysfunction, mild hepatic encephalopathy (HE) particularly grade 1 HE may not be consistently reproducible using the West Haven criteria, and as such is now included as part of the covert HE spectrum along with minimal HE [10] often requiring psychometric tests or EEG for diagnosis.

Additioally, post-hoc analysis of CANONIC data has identified rapidly progressive hyperbilirubinaemia with a serum bilirubin level greater than 20 mg/dL at the time of presentation as a single hepatic organ failure being associated with poor prognosis. This criterion was also used in the RELIEF study, the only randomized controlled trial to date of MARS therapy in ACLF [11].

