5.2. Investigational device exposure

For the randomization an Interactive Wireless Randomization System (IWRS) is used, which is linked to the study data base. Randomization is automatically assigned through the IWRS system. Patients are randomised to either the DIALIVE or SOC arm in a 1:1 ratio.

¹¹ The prismaflex platform will be provided by Yaqrit to those sites that do not have access to such haemofiltration machines. The machine will remain the property of Yaqrit Ltd during and after the study. A mainenance agreement in such circumstances will be established with each institution.

Patients will be assigned into five (5) Cohorts. Each cohort will consist of six (6) patients (3 DIALIVE: 3 SOC). If there are dropouts in any of the following cohorts during the study period, patients will be replaced in each of the cohorts described below to reach the appropriate number of 6 evaluable patients in each cohort.

Cohort 1: including 3 control and 3 DIALIVE treated patients. Cohort 2: including 3 control and 3 DIALIVE treated patients. Cohort 3: including 3 control and 3 DIALIVE treated patients. Cohort 4: including 3 control and 3 DIALIVE treated patients. Cohort 5: including 3 control and 3 DIALIVE treated patients.

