12.4. Procedures for recording and reporting Adverse Events and Device Deficiencies

12.4.1. Investigator responsibilities:

The site Investigator shall report any SAE, SADE, USADE and DDs which occur in a subject to the Sponsor/CRO immediately but no later than 3 calendar days after site awareness of the event. The immediate report for all events may be made orally or in writing (using the Sponsor's/CRO SAE form or DD form, as applicable) and shall be followed by a detailed written report on the event.

The PI will respond to any queries raised by the Sponsor/CRO as soon as possible.

The Sponsor/CRO will report any SAE or DD to the REC and/or Competent Authority according to national guidelines.

All deaths of a patient during their participation in the study will be reported as a SAE irrespective of whether the death is related to trial participation or an unrelated event.

Where the event reported consists of, or results in the death of a subject, the investigator shall supply the Sponsor/CRO with any additional information requested by the Sponsor/CRO. Where the death has been reported to the relevant ethics committee, the investigator shall supply any additional information requested by that committee. All serious adverse events will be recorded in the hospital notes, the eCRF and a SAE form.

The investigator shall keep detailed records of all adverse events and device deficiencies relating to the clinical investigation, which are reported to them, by trial participants or users. The investigator shall document all relevant information on Sponsor/CRO provided AE logs, SAE forms and DD forms.

12.4.2. Reporting of all Adverse Events and Device Deficiencies: Investigator and Sponsor responsibilities

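### The last scheduled survival contact may fall 5 days before Day 28 or Day 90, and no vital-status check on or after the landmark is required

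*Protocol*

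**What the plan says.** Section 5.1.3 lists "Mortality: 28-days and 90 days" among the secondary endpoints; the synopsis has the same item as 28 days and 3 months.

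Section 5.3.6 sets follow-up by cohort: "Patients from cohort 1, 2 and 3 are followed for 28 days, those from cohort 4 and 5 for 90 days". It adds that patients "complete the study after completion of study day 28 (cohort 1, 2 and 3) or day 90 (cohort 4 and 5".

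The schedules in section 5.4 give the Day 28 visit a window of plus or minus 5 days in the SOC table and in the main DIALIVE table. Day 90 has the same window, and its footnote reads "Survival data only via a telephone call". A further table, for DIALIVE patients during treatment, heads its Day 28 column with plus or minus 2 days.

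Deaths are also captured outside visits. Section 12.4.1 states: "All deaths of a patient during their participation in the study will be reported as a SAE", within 3 calendar days of the site becoming aware.

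Some patients have 28 days of follow-up for another reason: those whose treatment is discontinued (footnote 10 to section 5.1.2) and those with an incomplete dialysis cycle (section 5.1.7).

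**The concern.** A fixed-day mortality endpoint needs vital status known up to that day. A symmetric window lets a fully compliant last contact take place before it. A cohort 1-3 patient seen alive on Day 23 and dying at home on Day 26 is a 28-day death by definition, yet no scheduled contact would reveal it. The same holds for a cohort 4-5 patient telephoned on Day 85 who dies on Day 88.

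The error has one direction: an early contact can hide a death but cannot add one. With 15 evaluable patients per arm, and only 9 per arm in cohorts 1-3, a single unrecorded death visibly changes the reported percentage. An analysis plan can decide how to treat an early last contact, but it cannot recover a death that nobody ascertained.

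**Working it through.** **Inputs from the protocol**
- Cohorts: "Each cohort will consist of six (6) patients (3 DIALIVE: 3 SOC" (section 5.2), five cohorts. 5 x 6 = 30 evaluable patients, which reproduces the stated total. That total is not a power calculation; section 5.3.7 says "the sample size is arbitrarily set to obtain adequate information in a small patient population".
- Cohorts 1-3: 18 patients, 9 per arm. Cohorts 4-5: 12 patients, 6 per arm.
- 28-day mortality, for scale only: "mortality of 22%, 32% and 78% for ACLF grades 1, 2 and 3, respectively" (section 2.7).

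**Assumptions not in the protocol**
- Constant hazard up to the landmark.
- 90-day mortality of 30% to 60%.
- For the upper bound: every contact on its earliest day, and no death learned of afterwards.

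**Step 1: uncovered days.** 28 - 5 = 23 and 90 - 5 = 85. The days without a required check are 24-28 and 86-90.

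**Step 2: who is exposed.** For 28-day mortality, cohorts 1-3. In cohorts 4-5 the Day 90 call would show a death on Days 24-28, except in patients followed for only 28 days. For 90-day mortality, the 12 patients of cohorts 4-5.

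**Step 3: worst case at Day 28.** Hazard h = -ln(1 - m)/28; survival S(t) = exp(-ht); loss = S(23) - S(28).

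| 28-day mortality m | h per day | Observed if contact on Day 23 | Loss | Share of deaths lost | Expected among 18 |
|---|---|---|---|---|---|
| 22% | 0.00887 | 18.5% | 3.5 points | 16.1% | 0.64 |
| 32% | 0.01377 | 27.2% | 4.8 points | 15.2% | 0.87 |
| 78% | 0.05408 | 71.2% | 6.8 points | 8.8% | 1.23 |

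**Step 4: visits spread evenly over Days 23 to 33 (11 days).** Only visits on Days 23-27 lose anything, so the mean loss is the sum of S(v) - S(28) for v = 23 to 27, divided by 11.
- m = 22%: (0.0354 + 0.0282 + 0.0210 + 0.0140 + 0.0070)/11 = 0.0096. Observed mortality is 21.0%; 0.0096/0.22 = 4.4% of deaths lost; 18 x 0.0096 = 0.17 deaths.
- m = 32%: (0.0485 + 0.0385 + 0.0287 + 0.0190 + 0.0094)/11 = 0.0131. Observed mortality is 30.7%; 0.0131/0.32 = 4.1% of deaths lost; 18 x 0.0131 = 0.24 deaths.

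**Step 5: worst case at Day 90.** With h = -ln(1 - m)/90, S(85) - S(90) is 0.0140 for m = 30% and 0.0209 for m = 60%. Among 12 patients that is 0.17 to 0.25 expected deaths.

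**Step 6: weight of one death.** 1/9 = 11 points in a cohort 1-3 arm, 1/15 = 6.7 points in a full arm, 1/6 = 17 points in a cohort 4-5 arm.

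**The case against.** The strongest reply is that the protocol does not end follow-up at the early contact. Section 5.3.6 ties completion to the end of study Day 28 or Day 90, and a death before then is a reportable SAE. Section 5.5 adds full source verification of reported SAEs and a monitoring check that sites tried repeatedly to reach patients considered lost. Length-of-stay endpoints at Day 28 and Day 90 also give sites a reason to know where a patient is. All of this stands, and it rules out reading the plan as releasing patients on Day 23. It does not close the gap. The reporting duty starts with site awareness, and a discharged patient seen within the window is not lost to follow-up, so nothing prompts a further check.

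A reader might infer that such a patient would be counted as a survivor. The protocol contains no such rule. It excludes imputation and analyses the data available, and how an early last contact is classified may be set in the statistical analysis plan.

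A reader might also infer unequal loss between arms from the plus or minus 2 days in one DIALIVE table. The document does not support this. That table covers sampling and monitoring during treatment, and as printed it has no adverse-event or survival row and no entry under Day 28. The adverse-event row sits in the main schedules, where the window is 5 days for both arms.

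Finally, the 15-16% figure is an upper bound and the constant hazard is unsupported. Appendix 7 reports two DIALIVE deaths within 24-36 hours of starting treatment; if deaths cluster early, fewer fall on Days 24-28.

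**Conclusion.** The gap is real but modest. A compliant last contact can precede the landmark by up to 5 days, and no text requires vital status on or after it. This affects 28-day mortality in cohorts 1-3 (18 of 30 evaluable patients) and in any patient followed for only 28 days, and 90-day mortality in cohorts 4-5.

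The realistic size at 22% to 32% mortality is about 0.2 expected deaths among the 18. The bound is 0.64 to 0.87, and it needs every visit on Day 23 and no news of a death by any other route. Both figures rest on the constant-hazard assumption. The bias is always towards lower mortality.

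Mortality is a secondary endpoint and the protocol plans no statistical test, so no formal decision depends on it. The point is a worthwhile, cheap improvement and does not threaten the trial's main results. The differing Day 28 window in the during-treatment table is a clerical inconsistency.

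**What to change.** Leave the clinical visit windows as they are. Add a footnote to the schedules requiring vital status, with date of death where applicable, by telephone or record check on or after Day 28 and on or after Day 90. A window of 0 to +5 days for the survival item alone would do this. State that mortality is classified by date of death. Cohorts 1 and 2 had already been through DSMB review when this version was written, so for patients past the visit the check should be made retrospectively from records.

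Separately, make the Day 28 column heading in the DIALIVE during-treatment table agree with the other schedules.

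The cost is one footnote, one corrected heading, and a short call or record check for patients whose last contact came before the landmark.
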